Study design	This is a non-randomized, open label, single arm, multi-center, Phase II study to evaluate the efficacy and safety of eltrombopag in combination with IST regimen of r-ATG + CsA in East-Asian patients with SAA who have not received prior IST. Eligible patients will receive eltrombopag concomitantly with immunosuppressive therapy of r-ATG and CsA during the first 6 months. Responders at Week 26 are eligible to the extension part in which eltrombopag treatment will be provided up to Week 52. All participants will be followed up to Year 3 for survival and clonal evolution.

Population	This study population is East-Asian adult and pediatric patients (≥ 6 years old) with SAA who have not received prior immunosuppressive therapy. Thirty-six participants will be enrolled from China, Japan, Korea or Taiwan. Six pediatric participants will be recruited in total, with 3 from China and 3 from Japan. At least one of the 6 pediatric participants in each age group (6 to 11 years old, and 12 to 17 years old) will be enrolled. For the 30 adult participants, at least 12 participants will be recruited from China to fulfill the requirements for PK profile.
Key Inclusion criteria	
 Written study informed consent and (where applicable) assent from the participant, parent, or guardian must be obtained prior to participation in the study. Participants of East Asian ancestry aged ≥ 6 years old at the time of written informed consent and assent form (if applicable). SAA characterized by: 
 Bone marrow cellularity < 25%, or 25-50% with < 30% residual hematopoietic cells and pancytopenia, with at least two of the following parameters in peripheral blood: 
 Absolute neutrophil count < $0.5 \times 10^9/L$ Platelet count < $20 \times 10^9/L$ Absolute reticulocyte count < $20 \times 10^9/L$ HSCT is not suitable or available as a treatment option (determined as per local practices or national guidelines), or has been refused by participant.

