As per [Section 4.6](#), during a Public Health emergency as declared by Local or Regional authorities i.e. pandemic, epidemic or natural disaster that limits or prevents on-site study visits, alternative methods of providing continuing care may be implemented by the investigator as the situation dictates. If allowable by a local Health Authority and depending on operational capabilities, phone calls, virtual contacts (e.g. tele consult) or visits by site staff to the

participant's home, can replace on-site study visits, for the duration of the disruption until it is safe for the participant to visit the site again.

Table 8-1 Assessment Schedule

Period	Screening	Core treatment part												Extension part		EOT		Long-term Follow-up	
Visit Name	Screening	Day 1	Week 1	Week 2	Week 3 / 5 / 7	Week 4 / 8	Week 6	Week 9/11/15/17/19/21/23/25 when dose adjusted		Week 10/12/14/16/18/20/22/24		Week 13	Week 26	Week 28 to Week 50 ¹	Week 52	End of treatment	Safety follow-up	Survival follow-up	Year 2 / Year 3
Days	-30 to -1	1	8	15	22 / 36 / 50	29 / 57	43	64 to 176		71 to 169		92	183	197 to 351	365	EOT	30 days after EOT	every 3 months	729 / 1093
Informed consent	X																		
Demography	X																		
Medical history/current medical conditions	X																		
Characteristics of SAA	X	X																	
Inclusion / Exclusion criteria	X	X																	
Supportive therapy	X	X	X	X	X	X	X	X		X	X	X	X	X	X			X ²	
Concomitant medications	X	X	X	X	X	X	X	X		X	X	X	X	X	X	X			
Incidence of transfusion	X	X	X	X	X	X	X	X		X	X	X	X	X				X ²	
Physical Examination	Full body examination	S	S	S	S	S	S	S		S	S	Full body examination	S	Full body examination	Full body examination	S			
Vital Signs	X	X	X	X	X	X	X	X		X	X	Once a month	X	X	X				

Period	Screening	Core treatment part											Extension part		EOT		Long-term Follow-up	
Visit Name	Screening	Day 1	Week 1	Week 2	Week 3 / 5 / 7	Week 4 / 8	Week 6	Week 9/11/15/17/19/21/23/25 when dose adjusted	Week 10/12/14/16/18/20/22/24	Week 13	Week 26	Week 28 to Week 50 ¹	Week 52	End of treatment	Safety follow-up	Survival follow-up	Year 2 / Year 3	
Days	-30 to -1	1	8	15	22 / 36 / 50	29 / 57	43	64 to 176	71 to 169	92	183	197 to 351	365	EOT	30 days after EOT	every 3 months	729 / 1093	
ECOG or Lansky performance status	X																	
Height	X													Pediatric participants	Pediatric participants	Pediatric participants		
Body Weight	X									X	X		X	X				
Standard 12 lead ECG	X ³	X ³								X	X		X	X				

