8.1 Screening

All participants will be screened for study eligibility. All participants must sign an informed consent prior to any screening procedures being performed.

Activities for screening will begin up to 30 days prior to initiation of study treatment with eltrombopag, r-ATG and CsA. During this time, all participants will complete a bone marrow aspirate and biopsy to confirm current SAA diagnosis. The sample of bone marrow aspiration and biopsy, and the result of cytogenetic analysis obtained within 30 days prior to Day 1 can be used for evaluation, and the results will be used as baseline value. The criteria for diagnosis of SAA are found in [Section 5.1](#). Cytogenetic analysis and all other analyses will be completed to verify inclusion and exclusion criteria.

An evaluable karyotyping is mandatory for the eligibility assessment. Eligibility must be based on a normal karyotype of at least 10 metaphases. If 10 metaphases are not seen, the bone marrow aspirate must be repeated. The participant won't be eligible if the karyotyping fails again by the second bone marrow aspiration due to insufficient metaphases.

In addition to conventional karyotyping, FISH should be performed to detect abnormalities in chromosome 3, 5, 7, 8 and those associated with SAA, MDS, acute myeloid leukemia (AML) etc. Candidate participant may start with the investigational treatment if a normal karyotyping result is shown for eligibility assessment while waiting for the FISH result. In case the FISH result comes out to be abnormal indicating cytogenetic abnormalities, the participant must be discontinued from the study treatment.

Information regarding eligibility criteria will be collected on the Inclusion/Exclusion eCRF. Participants who do not meet all entry criteria should not be entered into the study.

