8.2 Participant demographics/other baseline characteristics

Participant demographic and baseline characteristic data to be collected on all participants include:

- Demographic information: age, gender, predominant race and ethnicity
- ECOG or Lansky performance status, height (cm) and weight (kg), body temperature (°C), blood pressure (mmHg) and pulse rate (bpm).
- Date of diagnosis, severity etc. of aplastic anemia.
- Prior and concomitant medications and transfusion history (Within 60 days prior to Day 1).
- Clinically significant findings in a complete physical examination (see [Table 8-2](#)) during the screening period.
- Laboratory evaluations: peripheral blood smear, bone marrow aspiration and cytogenetic analysis, flow cytometry of CD34-positive cells from bone marrow aspiration, bone marrow biopsy, FISH, hematology and chemistry test, blood coagulation test, pregnancy test, hepatitis and HIV screen, serum folate and vitamin B12, iron panel, thyroid function, and flow cytometry of the peripheral blood for glycosylphosphatidylinositol (GPI)-cells.
- Imaging evaluations: chest X-ray, abdominal sonography, echocardiogram.
- Cardiovascular medical history and risk factors, ECG
- Cataract medical history and risk factors
- Medical history (all important medical, surgical, and allergic conditions that could have an impact on the participant's evaluation before signing the informed consent) / current medical conditions (e.g. all relevant current medical conditions which are present at the time of signing informed consent). Ongoing medical conditions, symptoms and diseases which are recorded on the Medical History eCRF should include the toxicity grade when applicable.

Procedures conducted as part of the participant's routine clinical management (e.g. blood count) and obtained prior to signing of informed consent may be utilized for Screening or baseline purposes provided the procedure meets the protocol-defined criteria and has been performed in the timeframe of the study. Due to the nature of SAA, blood counts may fluctuate depending on transfusions, so the baseline count is defined as follows:

- The hematology assessed at the time of diagnosis will be used for screening and as baseline count.

- If the assessment at the time of diagnosis is unavailable, the lowest value available within 30 days before Day 1 will be used as the baseline count.

Baseline platelet transfusion independence/dependence are defined as:

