8.3 Efficacy

Efficacy assessments include hematologic results, transfusion data, assessment of relapse and survival.

Hematologic parameters will be assessed at Screening, weekly from Week 1 to Week 8, then every 2 weeks to Week 26 (weekly until stabilization of the dose), then every 4 weeks until the end of eltrombopag treatment (every 2 weeks until stabilization of the dose) and yearly during the post-treatment follow-up (up to Year 3). Hematologic parameters will also be assessed as per the investigator decision to assess the maintenance of the response, relapse or for safety reasons.

Transfusion data will be recorded for any transfusion administered during the 60 days prior to treatment start and until the end of eltrombopag treatment for all participants who discontinue eltrombopag due to non-response at W26, relapse or alternative SAA treatment, and until the completion of study follow up for all the other participants. The date and time, content and number of units of each transfusion will be recorded.

Relapse will be determined according to the definition in this section by investigator and will be recorded into eCRF.

All participants will be followed for survival status every 3 months regardless of treatment discontinuation reason up to Year 3 until study completion, death, lost to follow-up, or withdrawal of consent for survival follow-up. Survival information can be obtained via phone, and information will be documented in the source documents and relevant eCRFs.

Hematologic response assessment will be performed by investigators at Week 13, Week 26, Week 52 and yearly after. At Week 13 and Week 26, responses assessment needs to be confirmed by two serial blood count measurements performed 1-3 weeks apart.

Response is defined as blood counts no longer meeting the standard ("Camitta") criteria (Camitta et al 1975) for severe pancytopenia in SAA, equivalent to 2 of the following values (Scheinberg et al 2009).

- Absolute neutrophil count $\geq 0.5 \times 10^9/L$
- Platelet count $\geq 20 \times 10^9/L$
- Reticulocyte count $\geq 20 \times 10^9/L$

A CR will be defined as (all 3 must be met):

- Absolute neutrophil count $> 1.0 \times 10^9/L$
- Platelet count $> 100 \times 10^9/L$
- Hemoglobin $> 100 \text{ g/L}$

A PR will be defined as blood counts that do not meet criteria for SAA but are not sufficient for a CR.

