### **Overall response (CR+PR) rate at Week 13, Week 26, Week 52 and yearly after**

Hematologic overall response rate at specific visit is defined as percentage of subjects who achieved hematologic response by investigator assessment at specific visit in FAS.

The overall hematological response is defined as either complete or partial response. CR is defined in [section 2.5.1](#).

Partial response (PR) is defined as blood counts no longer meeting the standard criteria for severe pancytopenia in SAA, equivalent to at least 2 of the 3 criteria below, but are not sufficient for a CR.

- Absolute neutrophil count  $\geq 0.5 \times 10^9/L$
- Platelet count  $\geq 20 \times 10^9/L$
- Reticulocyte count  $\geq 20 \times 10^9/L$

However, improvement in counts that are dependent upon exogenously administered growth factors or transfusion will not be considered as fulfilling response criteria.

The exclusion period of these therapies are detailed below:

- Platelets transfusions: 7 days preceding the assessment of platelet count
- Packed RBC transfusions: 14 days preceding the assessment of hemoglobin
- Growth factors: 21 days preceding the assessment of response.

Of note that the criteria for complete and partial responses must be met on 2 consecutive serial blood count measurements at least one week apart but not more than 4 weeks apart for the Week 13 and Week 26 assessments but only on one blood count measurements for the yearly assessments thereafter.

Patients who relapse or withdraw from the study will be counted and reported as relapsed or withdrawn for all subsequent response assessments. No response (NR) is defined as not fulfilling the response criteria.

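### Screening uses the counts at diagnosis with no age limit and PR needs no improvement from Day 1, so overall response may credit counts that left the SAA range before dosing

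*Protocol*

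**What the plan says.** **Entry.** Criterion 3 (Protocol summary and Section 5.1) combines marrow hypocellularity with a count rule, worded as "residual hematopoietic cells and pancytopenia, with at least two of the following parameters in peripheral blood": two or more of ANC <0.5, platelets <20 and reticulocytes <20 (all ×10⁹/L). No sampling date is attached to the counts.

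**Which counts.** Protocol 8.2: "The hematology assessed at the time of diagnosis will be used for screening and as baseline count". Only if these are unavailable does a 30-day limit apply, and then "the lowest value available within 30 days before Day 1 will be used as the baseline count".

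**Text that points the other way.**
- Section 8.2, shortly before that rule, lets pre-consent procedures be used "provided the procedure meets the protocol-defined criteria and has been performed in the timeframe of the study", with the blood count as its example.
- Section 8.1 says that in the 30-day screening period "all participants will complete a bone marrow aspirate and biopsy to confirm current SAA diagnosis", and refers to Section 5.1 for the diagnostic criteria.
- Table 8-1 schedules hematology and the row "Inclusion / Exclusion criteria" at both Screening and Day 1.
- Both SAPs (2.1.1) define baseline as the most recent value up to the start of study treatment, which is not the rule in Protocol 8.2.

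**Response.** Protocol 8.3: "A PR will be defined as blood counts that do not meet criteria for SAA but are not sufficient for a CR". SAP 2.7.1: "Partial response (PR) is defined as blood counts no longer meeting the standard criteria for severe pancytopenia in SAA", which it equates with two or more of the three counts at or above the entry cut-offs. Neither refers to the participant's own pre-treatment counts. Overall response is counted in the whole FAS, with no rule for someone who meets the response counts before dosing.

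**The concern.** With no control arm, overall response is read as what the regimen achieved. If the count that qualified a participant predates treatment by some time, and the counts have since risen above the SAA cut-offs, that rise is credited to eltrombopag + r-ATG + CsA.

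Three secondary results are exposed: overall response (Weeks 13, 26, 52 and yearly), time to response and duration of response. The last two are derived programmatically from laboratory values and share the same PR rule. Overall response at Week 26 also decides who may enter the extension part. It matters for interpretation too, because Protocol 1.1 supports the r-ATG combination by comparing overall response with history (57.1% against 37%).

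**Working it through.** **1. The plan's own figures.** Clopper-Pearson limits with n = 36 give 14/36 = 38.9% (23.1, 56.5), 16/36 = 44.4% (27.9, 61.9) and 18/36 = 50.0% (32.9, 67.1). The largest half-width is 17.08 points, at 18/36. All agree with Protocol Table 12-2 and SAP Table 3-1. Nothing in the sample size depends on the present point.

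**2. Entry and PR are complements.** Class each of the three counts as low or not low, which gives 2³ = 8 patterns.
- SAA count rule (two or more low): 3 patterns with exactly two low + 1 with all three low = 4.
- Response count rule (two or more not low): 3 patterns with exactly one low + 1 with none low = 4.
- The two sets do not overlap and together cover all 8.

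So anyone whose unsupported pre-dose counts fail the SAA rule, and who is not in CR, meets the PR count criteria. In three of the four SAA patterns, one count crossing its cut-off is enough. Example: ANC 0.7, platelets 25 and reticulocytes still below 20 have one low count, so the SAA rule fails and the PR counts are met.

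**3. Size for overall response.** Let m be the number already at PR counts before dosing, and p the response rate that would otherwise apply. Assume that all m remain at PR or better.

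Apparent rate = [m + (36 − m)p]/36, so net bias = apparent rate − p = m(1 − p)/36.

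The documents do not give m; 1 to 4 is an assumed range. Values of p come from Protocol 1.1: 37% (historical r-ATG + CsA), 50% (half of patients on r-ATG + CsA in a Chinese real-world study) and 57.1% (eltrombopag + r-ATG + CsA, Japanese study).

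| m | p = 37% | p = 50% | p = 57.1% |
|---|---|---|---|
| 1 | 1.75 | 1.39 | 1.19 |
| 2 | 3.50 | 2.78 | 2.38 |
| 3 | 5.25 | 4.17 | 3.58 |
| 4 | 7.00 | 5.56 | 4.77 |

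(Percentage points; for example 3 × 0.50/36 = 4.17.)

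**4. Gross maximum.** Each such participant fills one place in the numerator, 1/36 = 2.8 points. Three would turn 18/36 (50.0%; 32.9, 67.1) into 21/36 (58.3%; 40.8, 74.5), but only if none of the three would otherwise have responded.

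**5. What exclusion does.** With m = 3 and p = 50%, the apparent rate is (3 + 33 × 0.5)/36 = 19.5/36 = 54.2%. Leaving out the three gives 16.5/33 = 50.0%, so the bias is removed at the cost of three participants in the denominator.

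**6. Primary endpoint.** CR needs ANC >1.0, platelets >100 (×10⁹/L) and hemoglobin >100 g/L. Counts just above the SAA cut-offs are far from this.

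**The case against.** The best case against is that the protocol, read as a whole, already requires current disease. Section 8.1 confirms a current diagnosis by the Section 5.1 criteria, which include the counts; the proviso in 8.2 limits pre-consent blood counts to the study timeframe; and Table 8-1 repeats the eligibility check on Day 1. The diagnosis-count rule also has a stated reason, that transfusions make counts fluctuate.

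Much of this stands. A reader might infer that only the marrow has to be recent and that a participant with recovered counts is plainly eligible. The documents do not support that as fact; it is one reading of passages that pull in different directions. But none of them says that current counts must meet criterion 3, and the one specific sentence says the diagnosis counts are used. Transfusion-related fluctuation justifies using an unsupported or lowest count, not an undated one. A marrow examination screens out recovered marrow, but not a hypocellular marrow with non-severe counts.

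A reader might also infer from exclusion 1, which bars CsA only within 6 months, that diagnoses can be long past. The population is described as treatment naive, and no interval from diagnosis to treatment is given, so this remains a possibility only. The SAP does summarise time from diagnosis to first dose.

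The requirement for two serial counts at Weeks 13 and 26, and the transfusion and growth-factor exclusions, remove transient or supported rises. They do not remove a persistent one.

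**Conclusion.** The point holds as a risk of bias in secondary endpoints, arising from a stated rule and from passages that need reconciling. It is not evidence that overall response is inflated: no document shows a participant with recovered counts, and m may be zero.

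If there are such participants and they stay at PR, the net bias in overall response is about 1.2 to 1.8 points each for p between 57.1% and 37%, or about 4.2 points for three at p = 50%. The figure of 2.8 points each is tempting, but it is a gross ceiling that assumes none of them would have responded anyway. If some lose PR, the bias is smaller. No size can be put on time to response or duration of response from the documents.

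The primary CR result is not materially affected, and the trial tests no hypothesis. The reason to act is that the question can be settled from Screening and Day 1 hematology already collected.

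**What to change.** **Protocol.** Reconcile 8.1, 8.2, Table 8-1 and the SAP baseline definition on which counts establish eligibility and which serve as baseline. Enrolment is complete, so this now governs interpretation, and the working change is in the analysis.

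**SAP 2.7.1 and 2.7.2.**
- Classify each participant by the last pre-dose counts outside the exclusion periods of Protocol 8.3 (platelet transfusion 7 days, red cells 14 days, growth factors 21 days): SAA count criteria met, not met (flagged), or not assessable. The third category is needed because a transfused participant may have no unsupported count before Day 1.
- Report the number in each category. If none is flagged, say so.
- Add a supportive overall response rate at Weeks 13, 26, 52 and yearly, and a supportive duration of response, excluding flagged participants. Those not assessable stay in.
- Do not instead count flagged participants as responders only if they reach CR. That errs the other way: someone who goes from platelets 25 to 95 and ANC 0.7 to 2.0 would be called a non-responder.

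**Final-analysis SAP (11-Nov-2024).** Its Section 2.7 does not reproduce Week 13 and Week 26 overall response or time to response, so enter this explicitly as an added supportive analysis.

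**Cost.** One derived flag and a few supportive rows from existing data, a slightly smaller denominator, and possibly a slightly lower supportive rate.

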1.1 Background

Severe aplastic anemia (SAA) is a rare, life-threatening, acquired bone marrow failure disease characterized by tri-lineage marrow hypoplasia and a lack of hematopoietic stem and progenitor cells due to an immune-mediated attack on the bone marrow. The diagnosis of SAA is based on the exclusion of other disorders that can cause pancytopenia, with hypocellular bone marrow (< 25%, or 25-50% with < 30% hematopoietic cells) and pancytopenia (with at least 2 of the following: absolute neutrophil count (ANC) $< 0.5 \times 10^9/L$; platelet counts $< 20 \times 10^9/L$; reticulocytes $< 20 \times 10^9/L$) (Camitta et al 1975, Rosenfeld et al 2003, Marsh et al 2009). Aplastic anemia (AA) affects approximately 2 out of every 1 million people in western countries (Young and Kaufman 2008), and has a higher incidence in East-Asian countries (about 4-7 cases per million people) (Young et al 2006, Young and Kaufman 2008, Yang and Zhang 1991). The incidence of AA in China was reported as 3.3-7.4 per million, while that of SAA was 1.4-1.7 per million people (Wang et al 2011, Zhang et al 1999, Yang and Zhang 1991, Zhang et al 2001). A recent multicenter prospective study in China presented that among all AA patients enrolled, 61.9% were diagnosed as SAA, while 23.6% had very severe aplastic anemia (VSAA) (Zhu et al 2019). The incidence of AA in Taiwan is 5.67 per million people, with about half of the patients suffering from SAA or VSAA (Li et al 2019). In Japan the incidence of AA is 8.2 per million people (Ohta et al 2015).

Although the exact etiology of SAA remains unknown, clinical experiences and laboratory data suggest that the ultimate mechanism leading to development of bone marrow failure is immune mediated. Bone marrow suppression in AA is likely secondary to specific populations of effector T-cells. Activated cytotoxic T-cells expressing HLA-DR, the interleukin-2 receptor (CD25), and interferon- γ are elevated in SAA patients and localize in the bone marrow. Hematopoietic progenitor and stem cells are targets of the immune attacks by these cells. The effect exerted by cytotoxic T-lymphocytes are due, at least in part, to the Fas ligand-induced apoptosis of hematopoietic progenitor cells. Interferon- γ , in addition to its intrinsic inhibitory activity on hematopoietic progenitor and stem cells, can induce overexpression of Fas on target cells (Young et al 2006). Despite its often acute presentation, SAA is now recognized as an autoimmune disease which can become chronic with periodic flares of the immune process and the need to long-term immunosuppression in some patients. High resolution VB CDR3 analysis in patients with SAA shows significant increased non-random skewing of the V β -chain families of the T-cell receptor, indicative of disease specific clonal expansion (Risitano et al 2004). Furthermore, regulatory T-cell deficiency and TH1/TH17 mediated destruction of marrow elements corroborate an autoimmune pathogenesis, which has been reproduced in animal models (deLatour et al 2010, Solomou et al 2006, Solomou et al 2007, Scheinberg and Chen 2013, Kordasti et al 2012, Kook et al 2002, Risitano et al 2004, Tang et al 2010, Young and Maciejewski 1997).

The first-line treatment of choice is allogeneic hematopoietic stem cell transplantation (HSCT) for younger patients who are eligible and have an available donor; it is the preferred option when feasible as it is curative (Scheinberg and Young 2012, Georges et al 2018, Red Blood Cell Disease (Anemia) 2017). Yet less than 30% of patients are suitable candidates for optimal HSCT, and it is reported that only 3.98% of newly diagnosed SAA patients (including VSAA) in China received HSCT as the initial treatment, possibly because of the lack

of a matched sibling donor, the lead time to identify a suitable unrelated donor, age, comorbidities, or access to transplantation (Marsh et al 2009, Zhu et al 2019).

The standard regimen for treatment naive SAA patients who are ineligible for HSCT upfront, is immunosuppressive therapy (IST) comprising anti-thymocyte globulin (ATG) with Cyclosporin A (CsA). Although hematologic recovery with horse ATG (h-ATG)/CsA was observed in 60% to 70% patients, only a minority (about 10% historically) reached complete response (CR) (Scheinberg 2018, Scheinberg and Young 2012). One quarter to one third of the patients did not respond to h-ATG/CsA, and 30-40% of responders relapse (Scheinberg and Young 2012). Outcomes remain poor for patients who have an insufficient response to IST (Olnes et al 2012, Scheinberg and Young 2012).

In most Asian countries, only rabbit ATG (r-ATG) is available on the market, hence, r-ATG/CsA is recommended first-line treatment for patients with SAA in these countries (Red Blood Cell Disease (Anemia) 2017, Kojima et al 2011). Scheinberg et al 2011 and Marsh et al 2012 have reported that patient outcomes including survival were better with h-ATG compared with r-ATG, but studies from Asia had indicated similar responses to r-ATG and h-ATG in AA patients (Chuncharunee et al 2016, Suzuki et al 2016, Shin et al 2013). Recent real world study in China reported that half of the patients treated with IST of r-ATG/CsA achieved overall responses, with 9.4% achieved CRs (Zhu et al 2019), which is comparable with the findings from clinical studies in Asia that have demonstrated overall response rates of 58–70% (Chuncharunee et al 2016, Mahapatra et al 2015, Ramzan et al 2014). Incomplete responses, relapses, and primary refractoriness limit the success of this therapy. This highlights the unmet need to improve outcome following first-line IST in Asian patients.

Since the establishment of ATG/CsA as the initial treatment for SAA, there was a long hiatus in subsequent improvements to IST, with the notion that a "ceiling" had been reached in regard to exploring more intense immunosuppressive regimens in SAA (Passweg and Tichelli 2009). Intensification of primary IST for treatment-naive SAA patients with agents more immunosuppressive than h-ATG, including alemtuzumab, or high dose cyclophosphamide, have not been successful, and the additions of sirolimus or mycophenolate mofetil to h-ATG/CsA did not improve the response rates (Scheinberg et al 2006, Scheinberg et al 2009, Scheinberg et al 2012, Scheinberg 2018, Marsh and Kulasekararaj 2013). A likely limit to the efficacy of immunosuppression is the stem-cell deficit, from which the marrow is unable to recover after IST. Unfortunately, efforts to stimulate this primitive compartment, such as erythropoietin, granulocyte colony-stimulating factor (G-CSF), stem cell factor, and androgens, have been to no marked avail (Scheinberg and Young 2012, Marsh and Kulasekararaj 2013). Thus, other regimens are needed to address the limitations of IST for SAA patients ineligible for HSCT.

One of the most promising recent treatments for AA is the oral thrombopoietin (TPO) receptor agonist eltrombopag, which reported multilineage effect in refractory AA patients and improvement in hematological response when added to upfront IST (Desmond et al 2014, Townsley et al 2017). Eltrombopag interacts with the transmembrane domain of the TPO receptor (TPO-R) on megakaryocytes and human bone marrow progenitor cells, and increases hematopoiesis by inducing proliferation and differentiation of early bone marrow progenitor cells (Erickson-Miller et al 2010, Sun et al 2012). The multilineage effects of eltrombopag in

patients with AA may be through stimulation of bone marrow progenitor cells, as suggested by recent preclinical research ([Scheinberg 2018, Sun et al 2012](#)).

Efficacy and safety of eltrombopag in treatment naive SAA patients has been confirmed by the global pivotal study (NIH 12-H-0150/ELT116643/CETB115AUS01T/NCT01623167, hereafter referred to as Study CETB115AUS01T) - a non-randomized, single center, pilot phase I/II study investigating the IST regimen of h-ATG + CsA in combination with eltrombopag as experimental therapy in patients with SAA who have not received prior definitive IST. The study met its pre-specified primary objective. The complete hematological response rate (95% CI) at month 6 was 58.1% (39.1%, 75.5%) in Cohort 3 where all 3 drugs started concurrently on Day 1: h-ATG on Days 1-4, CsA and eltrombopag from Day 1 to month 6. Responding participants received low dose of CsA (maintenance dose) from month 6 to month 24.

Additionally, in the combined Cohort 3 + Extension Cohort, that used the same dosing regimen, 43.7% (33.1%, 54.7%) participants who had reached the month 6 visit or withdrew earlier were complete responders. The addition of a maintenance dose of CsA from Month 6 to Month 24 was implemented with protocol amendment 15 in participants who were responders at Month 6. It started with Participant CETB115AUS01T-046 in Cohort 2 and continued with all participants enrolled thereafter. In Cohort 2, responders who used maintenance dose of CsA (approximately half of participants enrolled) showed a longer median duration of overall response of 35.5 months vs. 26.0 months for participants who did not in this cohort, and a better relapse-free probability estimate at 1.5 years (80.0% vs 54.5%). The other cohorts used a different dosing schedule, and started eltrombopag on Day 14 with eltrombopag lasting for 6 months (Cohort 1) or for only 3 months (Cohort 2). They also met the primary endpoint but with lower CR rates: 33.3% (17.3%, 52.8%) and 25.8% (11.9%, 44.6%) in Cohort 1 and Cohort 2, respectively. The treatment regimen schedule where eltrombopag started concurrently with IST (h-ATG and CsA) on Day 1, lasted for 6 months with maintenance CsA from month 6 to month 24 showed the highest rate of improvement in hematological parameters, demonstrated an early, robust and consistent hematological recovery, with acceptable safety profile. Moreover, long-term survival for responders has been associated with an early and robust hematologic recovery ([Rosenfeld et al 2003](#)). In conclusion, the key benefits shown by adding eltrombopag to h-ATG/CsA based IST include the marked increase in the rate of complete hematological response at 6 months in all cohorts, with a higher CR rate of 43.7% in Cohort 3 + Extension Cohort (eltrombopag + h-ATG + CsA started on Day 1) which exceeded the historical rate of 10-25%. These data support the conclusion of a strong benefit risk for the addition of eltrombopag to h-ATG and CsA.

The clinical benefits derived from adding eltrombopag to ATG-based IST in this target population are independently substantiated by Study CETB115E1202 (also identified under GSK study code 201793; NCT02404025; hereafter referred to as Study CETB115E1202), a non-randomized, open label, single arm, Phase II study conducted in Japan evaluating the efficacy and safety of eltrombopag in combination with r-ATG + CsA in participants with moderate or more severe AA who had not received prior ATG/antilymphocyte globulin (ALG)-based IST. The addition of eltrombopag to r-ATG + CsA demonstrated that this treatment is an improvement over IST alone, showing better overall hematological response (57.1%) than the historical data with r-ATG + CsA alone in ([Scheinberg et al 2011](#)) at 6 months (37%), with acceptable safety profile consistent with that expected for participants with SAA and that

established of eltrombopag in the approved chronic immune thrombocytopenia (ITP), hepatitis C virus (HCV) and refractory SAA indications.

Eltrombopag in combination with IST (h-ATG/CsA) is approved for the first-line treatment of adult and pediatric patients (2 years and older) with SAA in the US (since 16-Nov-2018) and several other countries. In Japan, eltrombopag in combination with IST (r-ATG/CsA) is also approved for the treatment of AA patients who have not been treated with ATG (since 25-Aug-2017). In Taiwan and Korea, eltrombopag is already approved for the treatment of SAA patients who have had an insufficient response to IST.

